9.6 Study Masking and Minimisation of Bias

Randomisation of subjects aims to minimise potential selection bias.

Given a double-masked design is not feasible (i.e. treatment involves invasive surgical procedure under general anaesthesia), the sponsor, investigator and the subject will be

unmasked to whether a subject has been assigned to the AAV2-REP1 treatment groups, or the untreated Control group. However, within the treated groups, the sponsor, investigator and subject will be masked to the assigned dose $(1.0 \times 10^{-11} \text{ gp or } 1.0 \times 10^{-10} \text{ gp})$. To further minimise potential performance/detection bias, all subjective ophthalmic assessments at the Screening/Baseline Period (Visit 1) and from Month 1 (Visit 5) onwards, will be conducted by a masked (outcomes) assessor.

Additional measures to minimise potential performance/detection bias include standardised methodologies across participating sites (same equipment, assessor training/certification, surgical training), and an identical visit/assessment schedule for treated/untreated patients.

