9.6.1 AAV2-REP1 Treatment Groups vs Untreated Control Group, Assessor Masking

All ophthalmic assessments conducted during the Screening/Baseline period will be performed by appropriately qualified masked assessors. For the immediate post-operative visits, masking of the assessors will not be viable as clinical signs of surgery will be apparent (i.e. redness, swelling). Therefore, unmasked assessors will perform all ophthalmic assessments at Visit 3 (Day 1) and Visit 4 (Day 7). From Visit 5 (Month 1) onwards, masked assessors will be used, as any signs of surgery will have dissipated and it will not be possible clinically to differentiate between those subjects that have not undergone surgery, and those subjects that have undergone surgery and received active treatment.

Subjects randomised to the untreated Control group will not be required to attend the site at Visit 2, 3 or 4. As the key purpose of Visit 2 is surgery, and Visit 3 and 4, post-operative safety, there is limited utility in Control subjects attending. This will also limit the study burden for Control subjects, thereby potentially reducing the risk of subject withdrawal at this stage, and reducing the possibility of further unmasking due to direct contact and communication with fellow participants. Instead, a telephone contact from the site will occur for the Control group on Day 0 (Visit 2), Day 1 (Visit 3) and Day 7 (\pm 3 days; Visit 4).

In order to minimise bias further, masked assessors will not have access to the subject's medical records, source documentation or eCRF as data entries or notation (such as use of peri-operative corticosteroid) may be sources of unmasking. From Visit 5 (Month 1) onwards, the masked assessor will also read a pre-written statement to each subject, regardless of randomisation, reminding them of the masked nature of the study, and to avoid any reference to prior surgery/non-surgery, which eye may have received treatment or to allude to any information that may unmask the assessor as to which group the subject has been assigned to.

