13.7.1 Adverse Events

AEs will be coded using the Medical Dictionary for Regulatory Affairs version 21 or higher. Events will be summarised by system organ class, preferred term, and group. Both the number of eyes/subjects experiencing an AE and the number of events will be summarised. Similar summaries will be produced for study drug/procedure-related AEs, AEs leading to discontinuation, and SAEs. AEs will also be summarised by maximum severity, relationship to study drug/procedure, and time to onset and resolution.

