11.1 Adverse Events

Treatment-emergent adverse events (TEAEs) are defined as adverse events starting on or after the day of the surgery (or, for control subjects, Visit 2, Day 0). A pre-existing event that worsens in severity after Day 0 is treated as a new TEAE with date of onset set to the date of the increased severity. Summary tables will include TEAEs only. TEAEs will be summarized by eye (study eye vs non-study eye) for ocular events, by treatment (low dose, high dose and untreated control) and overall. Non-treatment emergent AEs will be listed only.

An ocular event is an event where the site of the event is reported as both eyes (OU), right eye (OD) or left eye (OS).

Proportion of subjects reporting an event will be calculated based on the number of subjects in the corresponding treatment group. The 95% CI will be calculated using the Clopper-Pearson method.

The number and percentage of subjects reporting any event, any non-ocular event, any ocular event, any ocular event in the study eye and any ocular event in the non-study eye will be summarized.

The summary of overall AEs (or SAEs) will be limited to TEAEs. All AEs will be coded using Medical Dictionary for Regulatory Activities (MedDRA) version 21.1 or higher.

An overall summary table of TEAE by treatment will be provided for the following categories:

- Number and percentage of subjects with a TEAE
- Number and percentage of subjects with a treatment-related TEAE
- Number and percentage of subjects with a serious TEAE
- Number and percentage of subjects with a treatment-related serious TEAE
- Number and percentage of subjects with a TEAE leading to death
- Number and percentage of subjects who discontinued due to a TEAE
- Number and percentage of subjects with a TEAE by severity
- Number and percentage of subjects with a TEAE by outcome
- Number and percentage of subjects with a TEAE by action taken

Adverse events will be summarized by treatment group and overall for subjects in the safety population. The following summaries of TEAEs will be provided:

- TEAEs by SOC and PT
- TEAEs by SOC and PT reported in \geq 5% in any treatment group

Biogen /	NightstaRx,	Ltd
RIIR111		

- TEAEs by SOC, PT, and maximum severity (missing severity, if any, will be counted as severe).
- Treatment-related (study drug or study procedure) TEAEs by SOC and PT
- Study procedure-related TEAEs by SOC and PT
- Study drug-related TEAEs by SOC and PT
- Serious TEAEs by SOC and PT

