- Treatment-related (study drug or study procedure) serious TEAEs by SOC and PT
- Study procedure-related serious TEAEs by SOC and PT
- Study drug-related serious TEAEs by SOC and PT
- TEAE leading to death by SOC and PT

In the summary, subjects may be counted under multiple SOCs and PTs, but for each SOC and PT, subjects are only counted once. If a subject experiences the same AE at more than one severity, the most severe rating will be given precedence.

If a subject experiences the same AE at more than one relationship to study drug/procedure, causal relationship will be given precedence over no causal relationship. However, where a causal relationship is identified by the Investigator, the subject will be counted once within each sub-category (related to Study Drug, related to Study Procedure, related to both Study Drug and Study Procedure unknown). In the summary tables, related events are defined as events that are assessed by the investigator to be related to study drug/procedure/both or with an unknown relationship.

Separate additional summaries will be provided for adverse events classified as Ocular Inflammation and Visual Acuity Reduced. The lists of PTs assigned to Ocular Inflammation and Visual Acuity Reduced are provided in a separated document (BIIB111 Signal Detection Plan). The following summaries will be provided by treatment:

- Ocular Inflammation-related TEAEs by SOC and PT
- Ocular Inflammation-related TEAEs by SOC and PT, and by time to onset (≤30 days; >30 days)
- Visual Acuity Reduced-related TEAEs by SOC and PT
- Visual Acuity Reduced-related TEAEs by SOC and PT, and by time to onset (≤30 days; >30 days)

Imputation rules for partial dates are presented in Appendix 3.

Summaries presenting frequency of AEs by SOC and PT will be ordered by descending frequency of SOC in the High Dose group and then, within a SOC, by descending frequency of PT in the High Dose group.

The following listings will be provided:

- All AEs
- AEs reported by subjects who discontinued from the study due to an AE
- All SAEs

• AEs leading to death

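### SAP 11.1 leaves out the AE event counts and time to resolution that the protocol promises and keeps an onset split for only a few event groups, so its general TEAE tables pool periods of unequal and equal eye examination

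*SAP*

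**What the plan says.** **AE summaries promised.** Protocol 13.7.1, like the synopsis, commits to two things for AEs in general: "Both the number of eyes/subjects experiencing an AE and the number of events will be summarised", and "AEs will also be summarised by maximum severity, relationship to study drug/procedure, and time to onset and resolution".

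**AE summaries planned.** The overall table in SAP 11.1 is made up of numbers and percentages of subjects, including "Number and percentage of subjects with a TEAE by outcome". In the tables by system organ class (SOC) and preferred term (PT), a subject may appear under several terms, "but for each SOC and PT, subjects are only counted once". Timing appears in two by-treatment tables: "Ocular Inflammation-related TEAEs by SOC and PT, and by time to onset (≤30 days; >30 days" and "Visual Acuity Reduced-related TEAEs by SOC and PT, and by time to onset (≤30 days; >30 days". SAP 11.8 uses the same cut for these two groups and for hypersensitivity when it relates immunogenicity to safety.

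**Examination schedule.** Among its safeguards against bias, Protocol 9.6 lists "an identical visit/assessment schedule for treated/untreated patients", and SAP 3.5 repeats this. Protocol 9.6.1 then says: "Subjects randomised to the untreated Control group will not be required to attend the site at Visit 2, 3 or 4". Controls are telephoned instead (Protocol 10.2 to 10.4; footnote b of the schedule of procedures).

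**The concern.** Two things come together here.

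First, the SAP departs from the protocol's safety plan without saying so. Where it changes the protocol on purpose, it says so: SAP 7.4 declares and explains its correction of the per-protocol definition. SAP 11.1 has no such statement.

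Second, timing and duration carry much of the meaning of an AE after vitrectomy and sub-retinal injection. Protocol 5.4 expects complications that may be transient or permanent. Protocol 12.3.1.2 itself uses recovery by the Month 1 visit to separate one kind of early vision loss from another. A count of subjects by outcome does not show how long an event lasted. A count without an onset split does not show whether an event arose in the weeks when only treated eyes had scheduled examinations, or later when all arms were examined alike. At stake is how far a difference in ocular TEAEs between treated and control subjects can be read as a difference in harm rather than in looking.

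**Working it through.** **1. The two documents side by side**

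| Summary | Protocol 13.7.1 | SAP 11.1 |
|---|---|---|
| Subjects with an AE | Yes | Yes, once per SOC and PT |
| Number of events | Yes | Not listed |
| Time to resolution | Yes | Not listed; only subjects by outcome |
| Time to onset | Yes, for AEs in general | 30-day split for two event groups (SAP 11.8 adds hypersensitivity) |
| Maximum severity, relationship | Yes | Yes |

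Two summaries are absent and one is narrowed.

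**2. Scheduled full ophthalmic examinations** (Protocol 10.2 to 10.8 and the schedule of procedures)

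| Period | Treated | Control |
|---|---|---|
| Day 0 | 1, before surgery (Protocol 12.1) | 0 |
| After surgery, before Month 1 (Days 1 and 7) | 2 | 0 |
| Months 1, 4, 8 and 12 | 4 | 4 |
| Total after surgery | 6 | 4 |

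Visual acuity and OCT are also measured in treated subjects on Days 1 and 7. Controls are asked about AEs by telephone on Days 0, 1 and 7 (Protocol 12.3.2). Unscheduled visits can add examinations in any arm.

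**3. What unequal examination alone could do (illustration)**

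The documents give no rate of findings per examination. Assume the same chance q in both arms, independent between examinations. The chance of at least one recorded finding in k examinations is 1 − (1 − q)^k.

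| Assumed q | Treated, k = 6 | Control, k = 4 | Months 4, 8 and 12 only, k = 3, either arm |
|---|---|---|---|
| 1% | 5.9% | 3.9% | 3.0% |
| 3% | 16.7% | 11.5% | 8.7% |
| 5% | 26.5% | 18.5% | 14.3% |
| 10% | 46.9% | 34.4% | 27.1% |

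For q = 5%: 1 − 0.95^6 = 26.5%; 1 − 0.95^4 = 18.5%; 1 − 0.95^3 = 14.3%. With no true difference per examination, a whole-study table would still show a gap of 2.0 to 12.5 percentage points over this range. A table limited to the visits after Month 1 would show none.

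**4. How well a 30-day cut matches the change in examination**

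Taking Month 1 as 30 days, the ±7-day window runs from 23 to 37 days after Day 0. SAP 5.3 counts the treatment day as Study Day 1, so this is Study Day 24 to 38. A finding first seen at the Month 1 visit can therefore fall on either side of the cut.

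**The case against.** The strongest reply is that much of this information appears elsewhere.

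- **Time to onset.** A reader might infer that the SAP drops it and cannot separate the first month at all. The documents do not support that: SAP 11.1 keeps the split, by treatment, for the two event groups it singles out. SAP 11.8 repeats it and counts an event that recurs in both periods in both.
- **Masking of late harm.** A reader might infer that early surgical events hide late ones generally. They do not. Counting is once within each SOC and PT, and ocular events are shown by study and non-study eye, so a redness event on Day 1 does not hide a later cataract. Saturation threatens the any-ocular-event row and perhaps broad SOC rows. What is lost within a PT is recurrence and timing.
- **Early surveillance of controls.** A reader might infer that controls go unobserved, or count 3 examinations against 0. Controls are asked about AEs by telephone, and the Day 0 examination precedes surgery. The post-operative imbalance is 2 v 0, in examination rather than in questioning.
- **Examination summaries.** SAP 11.3 to 11.6 summarise pressure, slit-lamp findings, lens grades and ophthalmoscopy by visit and treatment, and SAP 5.1 names Baseline and Months 1, 4, 8 and 12 as summary visits. SAP 11.8 also counts eyes with a loss of 15 letters or more at Month 12.
- **The schedule sentence.** Protocol 9.6.1 discloses and justifies the difference straight away.

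These replies narrow the point but do not remove it. Examination tables show findings, not AE severity, relatedness or duration, and SAP 11.3 omits the breakdown of pressure by eye in Protocol 13.7.2. A listing of all AEs is not a comparative summary. The terms in the two event groups are held in a separate document, so the SAP does not show whether any cataract, pressure, macular or retinal AE gets an onset split. None of this explains why event counts and time to resolution are absent.

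**Conclusion.** The point holds as a mismatch between protocol and SAP with a moderate effect on how safety can be read. Event counts and time to resolution are missing without explanation, and time to onset is narrowed to selected event groups. The general and serious TEAE tables pool a period with 2 v 0 scheduled post-operative examinations and a period with 4 v 4. In the treatment-related tables the comparison with control hardly arises, because Protocol 12.3.2 classes an event without exposure as unrelated; there the loss is of timing and duration in treated subjects.

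The size of any distortion is unknown. The gap of 2.0 to 12.5 points rests on assumed, equal and independent chances of a finding at each scheduled examination, and on no contribution from telephone contacts or unscheduled visits. Safety is descriptive and untested (Protocol 13.7, SAP 11), and the efficacy analyses are not affected. The change should be made, but the trial's main conclusion does not depend on it.

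**What to change.** 1. In SAP 11.1, restore the number of events and the time to resolution (or unresolved at last visit) for study-eye ocular TEAEs. If other AEs are to stay without these summaries, say so and give the reason, since Protocol 13.7.1 promises them for AEs generally.
2. Extend the existing ≤30/>30-day onset split to all study-eye ocular TEAEs and to serious TEAEs.
3. Note the limit of the split beside the tables. A condition seen on Day 1 or 7 in a treated eye counts as early, while the same condition first found at a control's Month 1 examination may be dated late. The split reduces unequal detection but does not remove it. Event counts do not remove it either, because they also reflect the closer early examination of treated eyes.
4. Correct Protocol 9.6 and SAP 3.5 to say that visits and assessments follow the same schedule in all arms from Month 1 onwards only.

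The cost is a few more descriptive tables and one corrected sentence in each document. No new data are needed: onset date, end date and outcome are already recorded for each AE (Protocol 12.3.2).

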11.2 Vital Signs

Blood pressure, pulse and change from baseline will be summarized by visit and by treatment.

11.3 Intraocular Pressure

Intraocular pressure and change from baseline will be summarized by visit and by treatment.

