5.4 Benefit / Risk Assessment

No treatment currently exists for CHM.

The non-clinical studies conducted with AAV2-REP1 showed that it provides efficient and functional transgene expression in CHM mouse and human cells, as well as in mouse and human RPE and photoreceptors, without overt toxicity. Results from the 26-week single-dose combined toxicity/biodistribution study conducted in rats indicate that administration of AAV2-REP1 by single sub-retinal injection to both eyes is well tolerated at dose levels of 1×10^{9} and 6×10^{9} gp/eye (equal to 1×10^{11} and 6×10^{11} gp/eye in humans) when evaluated 4 and 26 weeks after injection. Minor reductions in some ERG parameters, ocular inflammation, and microscopic signs of retinal/corneal degeneration were observed and were considered procedure-related or not biologically significant.

In humans, application of AAV2-REP1 to the surface of the retina requires retinal detachment via vitrectomy. The 2-step procedure employed in delivering AAV2-REP1 subretinally (see Section 9.4), allows the management of unexpected surgical complications of retinal detachment before the AAV2-REP1 is applied. Furthermore, since the volume of fluid required to detach the fovea is variable, by excluding the vector from the first step, and administering the vector after successful retinal detachment has been achieved, a precise, consistent dose in terms of genome particles can be applied into the sub-retinal space. Sub-retinal injection of AAV2-REP1 does carry the risks associated with vitrectomy and retinal detachment, which include intra-operative and post-operative complications; infection (most notably infectious endophthalmitis); low and elevated IOP; choroidal detachment; persistent retinal detachment, retinal tears, holes and breaks; macular hole and macular oedema; vitreous haemorrhage; visual impairment; metamorphopsia; and photopsia (Park 1995; Thompson 1996; Banker1997; Cheng 2001; Anderson 2006; Stein 009; Recchia 2010). Post-operative intraocular inflammation caused by vitrectomy is often associated with transient and sometimes permanent visual impairment. Another complication of vitrectomy is cataract formation, which may require an additional surgical procedure (cataract extraction) (Park 1995; Cheng 2001; Recchia 2010). In addition, the surgical procedure is performed under general anesthesia, which includes the risks of dizziness, confusion, nausea and vomiting.

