10.10 Unscheduled Visits

If clinically indicated, subjects may need to return to the site for an unscheduled visit. At a minimum, the following assessments will be performed.

• BCVA

- Full ophthalmic examination, including IOP, a slit-lamp examination, lens opacity, and dilated fundus examination
- SD-OCT
- AF
- AE/SAE monitoring
- Concomitant medication, procedures, and treatment review

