13.7.2 Full Ophthalmic Examination

Intraocular pressure and change from Baseline in IOP will be summarised by visit, by treatment and by eye. Abnormal slit lamp examination findings and dilated ophthalmoscopy findings, and shift from Baseline will be summarised by visit, by treatment and by eye.

Lens opacity categories and shift from Baseline will be summarised by visit, by treatment and by eye.

13.7.3 7-Field Colour Fundus Photography

Categories of colour fundus photography findings and shift from Baseline will also be summarised by visit, by treatment and by eye.

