5 GENERAL ASPECTS FOR STATISTICAL ANALYSIS

5.1 General Methods

All analyses and summaries will be produced using SAS® version 9.4 (or higher).

For descriptive summary statistics, the efficacy and safety data will be summarized and displayed by treatment groups (Control, Low Dose, High Dose) and visits (Baseline, Month 1, 4, 8, 12, and End of Study).

Summary statistics will be presented for continuous variables, by way of number of subjects, mean, standard deviation (SD), median, first and third quartiles (Q1 and Q3, respectively), 5th and 95th percentiles (P05 and P95, respectively), minimum and maximum. Where specified, the 95% Confidence Interval (CI) of the mean will be calculated. Summary statistics will be presented where appropriate by treatment and nominal visit with an additional entry for the end of study.

For categorical variables (including binary variables), counts and percentages will be presented. Where specified, the 95% 2-sided CI for proportions will be calculated.

The listings, except the listing for screen failures, will include all randomized subjects in the database. In general, the subject listings will be sorted by treatment group, subject number, eye (starting with the study eye) and assessment date (and time, if applicable).

Data for unscheduled assessments will be included when calculating baseline values, selecting worst result for shift analyses, and for summary of normal/abnormal values. The safety summary of observed and change from baseline data will be performed by nominal (i.e., scheduled) visits. Unscheduled visits will be included in the analysis of End of Study, i.e., the last available non-missing treatment endpoint.

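### Post-baseline IOP readings from unscheduled visits enter no IOP summary unless they are the subject's last value, and no highest or lowest post-baseline IOP summary is planned

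*SAP*

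**What the plan says.** SAP 11.3 plans this for IOP and nothing else: "Intraocular pressure and change from baseline will be summarized by visit and by treatment". Protocol 13.7.2 plans the same two quantities: "Intraocular pressure and change from Baseline in IOP will be summarised by visit, by treatment and by eye". Neither section gives IOP a shift table, a category table or a worst-value table.

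SAP 5.1 sets the general rule: "The safety summary of observed and change from baseline data will be performed by nominal (i.e., scheduled) visits". Unscheduled data are also used for baseline and for "selecting worst result for shift analyses, and for summary of normal/abnormal values". One further exception is stated: "Unscheduled visits will be included in the analysis of End of Study, i.e., the last available non-missing treatment endpoint".

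Protocol 5.4 lists "low and elevated IOP" among the risks of vitrectomy and retinal detachment. Protocol 10.10 says "If clinically indicated, subjects may need to return to the site for an unscheduled visit", and makes the full ophthalmic examination, IOP included, part of the minimum set of assessments at such a visit.

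**The concern.** An unscheduled visit happens because something is clinically indicated, and IOP is always to be measured there. Under the SAP 5.1 rule that reading normally goes unused in the IOP tables. A transient rise or fall that has settled by the next reading leaves no trace in them.

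IOP is a named harm that can go in either direction. The natural descriptive question is how many eyes had a marked excursion at any time after surgery, and how large it was. Value and change at scheduled visits do not answer it. The IOP tables could look unremarkable in the operated arms while eyes had excursions between visits, and measured evidence on the harm would then give way to adverse event reporting. That reporting is done by an investigator who knows whether the subject was operated on (Protocol 9.6), and the visible text gives no IOP level for reporting.

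**Working it through.** The plan states no figure to reproduce. The check follows a post-baseline IOP reading from an unscheduled visit through each place it could be summarised.

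| Possible place | Rule | Does the reading enter? |
|---|---|---|
| IOP value and change by visit (SAP 11.3) | Nominal visits only (SAP 5.1) | No |
| Worst result in a shift table | Allowed by SAP 5.1, but SAP 11.3 plans no IOP shift table | No such table |
| Normal/abnormal summary | Allowed by SAP 5.1, but none is planned for IOP | No such table |
| End of Study row | Last available non-missing value (SAP 5.1) | Only if it is the subject's last |
| Adverse event tables (SAP 11.1) | Counts reported treatment-emergent events | Only if reported, and as an event rather than a measurement |

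Two illustrative subjects show how the End of Study exception works:

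- One has an extreme IOP at an unscheduled visit on Day 15, then ordinary readings at Months 1 to 12. His End of Study value is the Month 12 one. The Day 15 reading is in no IOP summary.
- The other has the same reading and then leaves the study with no further IOP. His Day 15 reading becomes the End of Study value and is summarised.

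For a subject who completes Month 12, the last reading is normally the Month 12 reading, so the exception is narrow.

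The visit windows in Protocol Table 3 show when only an unscheduled or early termination visit can yield an IOP. They are counted from Day 0, with a month taken as 30 days (an assumption):

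- Day 1 to Day 7 − 3 = Day 4: nothing scheduled on Days 2 to 3.
- Day 7 + 3 = Day 10 to Month 1 − 7 = Day 23: nothing scheduled on Days 11 to 22.
- Month 1 + 7 = Day 37 to Month 4 − 7 = Day 113: nothing scheduled on Days 38 to 112.
- Month 4 + 7 = Day 127 to Month 8 − 14 = Day 226: nothing scheduled on Days 128 to 225.
- Month 8 + 14 = Day 254 to Month 12 − 14 = Day 346: nothing scheduled on Days 255 to 345.

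Such gaps are ordinary in a trial. What matters is that readings taken within them are collected and then mostly not summarised.

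**The case against.** The strongest reply is that the harm already has a counting route. Protocol 12.3.2 requires questioning about adverse events at every visit, unscheduled ones included, and requires every event to be recorded. Protocol 12.3.1.1 defines an event to include any unfavourable sign. SAP 11.1 then tabulates treatment-emergent events by system organ class, preferred term, severity and relationship, by eye for ocular events, with Clopper-Pearson intervals. This stands: a reader might infer that IOP excursions between visits go uncounted altogether, and the documents do not support that. The route still depends on a judgement that the reading was untoward, and it gives no distribution of measured pressures. SAP 11.1 adds dedicated summaries for ocular inflammation and reduced visual acuity, but not for IOP.

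A reader might also infer that unscheduled IOP values never reach an IOP summary. The End of Study rule rules that out.

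Nor should it be said that scheduled-visit summaries would hide extremes behind a mean. SAP 5.1 prescribes the 5th and 95th percentiles, minimum and maximum, which show extremes at the visits that are summarised.

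Finally, it is tempting to say that unscheduled slit lamp, lens and ophthalmoscopy findings are counted while IOP is not. SAP 11.4 to 11.6 plan shift tables for those examinations, and SAP 5.1 permits unscheduled data when a worst result is selected. Those sections do not say that the shift is to the worst post-baseline result, however, and Protocol 13.7.2 describes shifts by visit. The contrast is plausible but not explicit.

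It is fair to add that safety analysis here is descriptive and that value plus change is what the protocol asked for.

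**Conclusion.** The point holds in a limited form. As written, a post-baseline IOP from an unscheduled visit enters no IOP summary unless it is the last available value, and no highest, lowest or category summary is planned for a named surgical risk. This follows from reading SAP 11.3 with SAP 5.1 and needs no assumption about data.

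Its practical size is unknown, because the documents give no frequency for unscheduled visits or for IOP excursions. If few such visits occur, or every relevant excursion is reported as an adverse event, little is lost. Error control, power and the primary analysis are unaffected. It is a gap in safety reporting worth closing before database lock, because the data are already collected.

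Two neighbouring matters are separate. SAP 11.3 omits the by-eye split in Protocol 13.7.2. SAP 5.1 also does not name Day 1 or Day 7 among its summary visits, although IOP is measured there in treated subjects.

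**What to change.** Add to SAP 11.3: *For each arm, and for study and fellow eyes separately, the highest and lowest post-baseline IOP and the largest rise and largest fall from baseline will be summarised descriptively, using all scheduled, unscheduled and early termination values. The number and percentage of eyes in reporting categories, fixed by the sponsor before database lock, will be given.* No cut-off is proposed here: the documents supply none, and the categories would serve reporting only.

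Add to SAP 5.1: *Unscheduled values are included when selecting the highest and lowest post-baseline IOP.*

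The cost is these short additions to the SAP and one or two descriptive tables from data already collected.

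The downside is unequal opportunity to record an extreme. Treated subjects are examined on site at Visits 2 to 4, whereas controls have telephone contacts. Say so in a footnote and add a version restricted to Month 1 onward. That version reduces the imbalance but does not remove it, since unscheduled visits after Month 1 may still differ between arms. It also leaves out the early post-operative period, including about Days 11 to 22, so it should accompany the all-visits table and not replace it.
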